Outcomes:	
Partial nephrectomy
 
PRIMARY
 
 Assess the presence and extent of fluorescence of cT1 RCC during partial nephrectomy 
SECONDARY
 
 Pathologic agreement of fluorescence and FR α by immunohistochemistry Agreement between visual and fluorescent images Inter-observer agreement of laparoscopic fluorescent images (for blinded surgeons) Surgeon opinion of usefulness of intra-operative fluorescence imaging-Likert scale questionnaire (Appendix A) Safety (perioperative, 10 days, 1-month)- Vital signs, hematology, chemistry, and adverse events (NCI-CTCAE v4.0)
	
Radical nephrectomy and lymph node dissection
 
PRIMARY
 
 Assess the presence and extent of fluorescence in regional lymph nodes or metastasis in patients with RCC 
SECONDARY
 
 Pattern of nodal spread Agreement of nodal and primary tumor fluorescence Pathologic agreement of fluorescence and FR α by immunohistochemistry Detection of RCC in primary tumor in situ Agreement between visual and fluorescent images. Inter-observer agreement of in-situ fluorescent images (for blinded surgeons) Surgeon opinion of usefulness of intra-operative fluorescence imaging- Likert scale questionnaire (Appendix A) Safety (perioperative, 10 days, 1-month)-Vital signs, hematology, chemistry, and adverse events (NCI-CTCAE v4.0)

LIST OF ABBREVIATIONS AND TERMS

[figure not shown]
Abbreviation/Term	Definition
ADE	Adverse device effect
AE	Adverse event
BMP	Basic metabolic panel
CBC	Complete blood count
CMP	Comprehensive metabolic panel
CRF	Case report form
CT	Computed tomography
CTMS	Clinical Trial Management System
CTO	Clinical Trials Office
CTSI	Indiana Clinical and Translational Sciences Institute
DSMC	Data Safety Monitoring System
ECOG	Eastern Cooperative Oncology Group
FDA	Federal Drug Administration
FR	Folate receptor protein
FITC	Fluorescein isothiocyanate
GFR	Glomerular filtration rate
IDS	Investigational Drug Service
IHC	Immunohistochemistry
IND	Investigational new drug
IUH	Indiana University Hospital
IUSCC	Indiana University Simon Cancer Center
LND	Lymph node dissection
REDCap	Research Electronic Data Capture
RCC	Renal cell carcinoma
SAE	Serious adverse event
SEER	Surveillance epidemiology and end results

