To further assess agreement of gross fluorescence with pathology, at least one representative lymph node biopsy done. Once the specimen is removed, it will be processed by the surgical team on the back table and sent to pathology for microscopic examination and immunohistochemistry assessment to determine if it contains FR α + cancer cells. The pathologist will be blinded to the fluorescence results of the tumor.

For All Surgeries

- Vital signs: recorded per institutional practice
- AE assessment: including hypersensitivity reactions, which could include skin reactions, difficulty breathing, eye or nasal reactions, or gastrointestinal complaints, redness, tenderness, pain, or rash at the injection site or any clinically relevant abnormality (with exception of surgical scars) that was not present at screening.
- Adverse device effects (ADE) assessment: the surgeon will examine the subject to confirm that there are no visible changes to skin (erythema or pigment darkening), tissue or organs related to fluorescence. Changes could be present but are likely due to the temperature of the cauterization as lesions are excised.
- Concomitant medications: record all intraoperative medications (this does not include normal saline or other routine maintenance intravenous fluids)

8.3.2.3 Post-surgery:

- Post-surgery questionnaire: the surgeon will complete a questionnaire describing the usefulness of the fluorescence imaging for tumor removal and to achieve a negative margin (**Appendix A**).
- Blinded surgeon assessment: A co-investigator, blinded surgeon who was not involved with the case will view the photographs and complete a questionnaire to assess inter-observer agreement (**Appendix A**).
- Type of RCC excision (radical, partial), need for blood transfusion and estimated blood loss
- Vital signs: recorded per institutional practice

- AE assessment: including hypersensitivity reactions, which could include skin reactions, difficulty breathing, eye or nasal reactions, or gastrointestinal complaints, redness, tenderness, pain, or rash at the injection site or any clinically relevant abnormality (with exception of surgical scars) that was not present at screening.
- ADE assessment: the surgeon will examine the subject to confirm that there are no visible changes to skin (erythema or pigment darkening), tissue or organs related to fluorescence.

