12.8 Analysis of secondary objectives

Specificity: The analysis for specificity is described above.

Detection of RCC in primary tumor (radical nephrectomy arm only): This analyses will be the same as for the primary objective in the partial nephrectomy arm. Pattern of nodal spread will be described qualitatively.

Agreement between pathological agreement between fluorescence and FR α by IHC: This endpoint will also be assessed by Kappa statistics (for presence/absence) or Intra Class Correlation (for numerical measures). Agreement between nodal and primary tumor fluorescence in the radical nephrectomy arm will be assessed similarly.

Agreement between visual and fluorescent images: Kappa statistics will be used to assess agreement between visual and fluorescent images. In addition, the number of lesions detected by

usual visible/tactile conditions and/or palpation vs fluorescent imaging will be analyzed using a paired t-test.

Inter-observer agreement: Kappa statistics will be used to assess inter-observer agreement between of captured fluorescent images.

Usefulness: Responses to the Likert scale questionnaire completed by the surgeons will be listed and summarized

Safety: Vital signs will be summarized using descriptive statistics. Clinical chemistry, hematology, and urinalysis laboratory values will be listed in tabular format and those with above or below normal range will be identified within the table. AEs and TEAEs will be summarized by body system and presented by severity and causal relationship to study drug. ADEs will be summarized by body system and presented by severity and causal relationship to study device. Patients experiencing serious AEs or serious ADEs will be listed and summarized in tabular format.

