19.1.1 Partial nephrectomy

Intraoperative surgeon assessment tool

Primary surgeon questionnaire: fill out immediately following completion of case.

1. What camera was used during the case?
 - a. da Vinci® Fluorescence Imaging Vision System
 - b. Visionsense VSiii 3DHD

2. At what time was the fluorescent camera first used during the case?
 - a. _____

3. List all organs or structures with fluorescence:
 - a. _____

4. Does the tumor show fluorescence?
 - a. Very bright fluorescence
 - b. Bright fluorescence
 - c. Mild fluorescence
 - d. Minimal fluorescence
 - e. No fluorescence

5. Does the normal kidney surrounding the tumor show fluorescence?
 - a. Very bright fluorescence
 - b. Bright fluorescence
 - c. Mild fluorescence
 - d. Minimal fluorescence
 - e. No fluorescence

6. Compare fluorescence between tumor and kidney:
 - a. Tumor is a lot more than the kidney
 - b. Tumor is more than the kidney
 - c. Tumor is the same as the kidney
 - d. Tumor is less than the kidney
 - e. Tumor is a lot less than the kidney

7. Does fluorescence aid in locating the renal tumor?
 - a. Yes, a lot
 - b. Yes, somewhat
 - c. Not sure
 - d. No, somewhat worse than without fluorescence
 - e. No, a lot worse than without fluorescence

8. Does fluorescence help resect the tumor?
 - a. Yes, a lot
 - b. Yes, somewhat
 - c. Not sure
 - d. No, somewhat worse than without fluorescence
 - e. No, a lot worse than without fluorescence

9. Does fluorescence help to identify the border or margin of the tumor during resection?
 - a. Yes, a lot
 - b. Yes, somewhat
 - c. Not sure
 - d. No, somewhat worse than without fluorescence
 - e. No, a lot worse than without fluorescence

10. If commercially available would you use this fluorescent product for partial nephrectomies?
 - a. Yes, a lot
 - b. Yes, somewhat
 - c. Not sure
 - d. No, most likely not
 - e. No, for sure not

11. Based on white light examination after tumor removal, are there any visible changes to organs (erythema or pigment change)?
 - a. Yes, explain _____
 - b. No

12. Based on white light examination after tumor removal are there any visible changes to skin (erythema or pigment darkening)?
 - a. Yes, explain _____
 - b. No

Blinded surgeon assessment of intraoperative photos

To be completed by surgeons not involved in case

1. Photographs taken with and without fluorescent imaging just inside trocar showing hemi-abdomen: Gerotas, colon, and liver (right); colon, spleen, stomach (left).

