 - a. Place “X” over any fluorescing regions and draw outline of each fluorescing area
 - b. Place “O” on white light images over tumor areas and draw outline of suspected tumor.
2. Photographs with and without fluorescent imaging taken after Gerotas removed showing tumor and surrounding normal parenchyma.
 - a. Place “X” over any fluorescing regions and draw outline of each fluorescing area
 - b. Place “O” on white light images over tumor areas and draw outline of suspected tumor.
3. Photographs with and without fluorescent imaging taken during resection of tumor.
 - a. Place “X” over any fluorescing regions
 - b. Place “O” on white light images over tumor areas
4. Photographs with and without fluorescent imaging taken in tumor fossa after tumor removal.
 - a. Place “X” over any fluorescing regions and draw outline of each fluorescing area
 - b. Place “O” on white light images over tumor areas and draw outline of suspected tumor.

Ex-vivo assessment of removed tumor

Primary surgeon to complete on back table immediately following case. All images are in digital full color.

1. What camera was used for ex-vivo assessment?
 - a. da Vinci® Fluorescence Imaging Vision System
 - b. Visionsense VSiii 3DHD
2. Gross fluorescent images of specimen 90° from each other by rotating about central axis. Also, upper and lower pole images (6 faces of specimen).
3. Does the tumor show fluorescence?
 - a. Very bright fluorescence
 - b. Bright fluorescence
 - c. Mild fluorescence
 - d. Minimal fluorescence
 - e. No fluorescence
4. 5mm slices through specimen with both fluorescent and white light image of each slice. Calibration measurement in photo.
5. At least 1 representative sample will be sent of primary tumor for FR- α assessment

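### The planned inter-observer kappa is not well defined by what the forms collect: the raters are described inconsistently, and the operating and blinded surgeons share no item, unit or scale

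*Combined protocol and SAP*

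**What the plan says.** **Analysis.** Section 12.8 gives one sentence: "Kappa statistics will be used to assess inter-observer agreement between of captured fluorescent images". It is incomplete at the point where the raters would be named. It states no rating unit, categories, weighting, rule for matching marks, or handling of several photographs per patient.

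**Raters.** Section 8.3.2.3 provides one reader: "A co-investigator, blinded surgeon who was not involved with the case will view the photographs and complete a questionnaire to assess inter-observer agreement". The synopsis lists the endpoint as "Inter-observer agreement of laparoscopic fluorescent images (for blinded surgeons" for partial nephrectomy and "Inter-observer agreement of in-situ fluorescent images (for blinded surgeons" for radical nephrectomy, both plural. The blinded form in Appendix A (19.1.1 and 19.1.2) is headed "To be completed by surgeons not involved in case", also plural.

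**Blinded form.** For four photograph sets, the reader places an X "over any fluorescing regions and draw outline of each fluorescing area", and an O on the white-light images over suspected tumour. Set 3 in the partial nephrectomy arm asks for marks without outlines. There is no graded or yes/no item.

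**Operating surgeon's records.** The Appendix A questionnaire asks, among other items, "Does the tumor show fluorescence", with five answers from very bright to none, and "List all organs or structures with fluorescence" as free text. Under section 8.3.2.2 this surgeon also marks suspected lesions with O and x on a schematic.

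**Status.** The endpoint is secondary in both arms (section 12.4). Section 3.3 hypothesises strong agreement between surgeons on what fluoresces. No target kappa is set.

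**The concern.** Kappa compares two or more raters who each classify the same fixed list of units into the same categories. The plan does not settle who the raters are, and the forms do not fix the units. If the pair is the blinded and the operating surgeon, they answer different questions, on different media, on different scales. If the pair is two blinded surgeons, they share a form, but free marking still gives no fixed list of regions.

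The analyst would then have to choose the unit and categories after seeing the marks, and the reported kappa could move widely with that choice. The hypothesis of strong agreement would be judged on a number that the plan does not determine.

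**Working it through.** The documents give no kappa, precision or sample-size figure for this endpoint, so there is no stated figure to reproduce. The check compares the instruments and then illustrates the consequence with assumed counts.

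**1. Instruments side by side**

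| | Operating surgeon | Blinded surgeon |
|---|---|---|
| Material rated | Live case; anatomical schematic | Captured photographs, four sets |
| Unit | Whole tumour or kidney; suspected lesion | Any area the reader chooses to mark |
| Scale | Five levels; free text; O/x | X, O, outlines |
| Meaning of X | Suspected tumour lesion seen under fluorescence | Any fluorescing region |

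No item appears on both forms in either arm. The X notation is common but the meaning is not. Section 19.4.7 accepts that normal kidney may take up the agent, so a blinded X on kidney does not contradict a schematic with no x there. The schematic in Appendix C could not be seen for this check, so whether it has fixed zones is unknown.

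**2. Region-level kappa**

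Let a = regions marked by both raters, b and c = regions marked by one only, d = regions marked by neither, n = a + b + c + d.

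- Observed agreement: po = (a + d)/n
- Chance agreement: pe = [(a + b)(a + c) + (c + d)(b + d)]/n²
- Kappa = (po − pe)/(1 − pe)
- Positive agreement = 2a/(2a + b + c)
- Negative agreement = 2d/(2d + b + c)

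Assume a = 8, b = c = 2. Free marks do not determine d.

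| d | Raw agreement | Kappa | Positive agreement | Negative agreement |
|---|---|---|---|---|
| 0 | 8/12 = 0.67 | -0.20 | 16/20 = 0.80 | 0 |
| 2 | 10/14 = 0.71 | 0.30 | 0.80 | 4/8 = 0.50 |
| 5 | 13/17 = 0.76 | 0.51 | 0.80 | 10/14 = 0.71 |
| 10 | 18/22 = 0.82 | 0.63 | 0.80 | 20/24 = 0.83 |
| 20 | 28/32 = 0.88 | 0.71 | 0.80 | 40/44 = 0.91 |
| 50 | 58/62 = 0.94 | 0.76 | 0.80 | 100/104 = 0.96 |
| 100 | 108/112 = 0.96 | 0.78 | 0.80 | 200/204 = 0.98 |

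For d = 10: po = 18/22 = 0.818, pe = (100 + 144)/484 = 0.504, kappa = 0.314/0.496 = 0.63. The same marks give any value in the kappa column, depending on how many unmarked regions are counted.

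**3. Patient-level presence/absence kappa, 10 patients in an arm (section 12.3)**

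- Both raters score 10 of 10 positive: pe = 1, so kappa is 0/0 and undefined.
- One rater scores 10 positive, the other 8: po = 0.80, pe = (10 × 8 + 0 × 2)/100 = 0.80, kappa = 0.
- Each scores 9 positive but they differ on the negative patient: po = 0.80, pe = (81 + 1)/100 = 0.82, kappa = -0.02/0.18 = -0.11. Positive agreement is 16/18 = 0.89.

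Mostly positive tumours are what the protocol expects. Section 3.3 cites 86% of RCCs as high positive for the receptor, and elsewhere up to 75% as up-regulated. If these shares held for tumour fluorescence, independently between patients, all 10 tumours would be positive with probability 0.86^10 = 0.22 or 0.75^10 = 0.06. Two accurate readers would then have no defined kappa.

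**The case against.** A reader might infer that kappa cannot be computed at all, that no paired ratings will exist, or that the operating surgeon gives only graded answers. The documents do not support any of these.

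- Presence/absence can be derived. The lowest grade of the tumour item against any higher grade could be paired with no X or an X over the tumour. The kidney item in Arm 1 and the free-text list could be paired with marks on the structures shown. Per patient, named structure or photograph set, no mark by either reader is a legitimate joint negative.
- The operating surgeon also records lesions with the O/x notation.
- The synopsis and Appendix A can be read as comparing several blinded surgeons, who would complete one form on the same photographs. The operating surgeon would then not be a comparator.
- The endpoint is descriptive, in a 20-patient pilot with no target kappa. Images are stored, and section 12 allows analysis changes without amendment unless a significant feature is altered.

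All of this stands, and it limits the point to definition and stability. It does not remove it. None of the derivations is planned, each is a choice among several, and each reduces the graded information to presence or absence. Several blinded readers would cure the difference between forms, but not the missing region list, and section 8.3.2.3 provides only one.

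**Conclusion.** The concern holds as a gap in definition that lies partly in the forms themselves. The rater pair is inconsistent between section 8.3.2.3 and the synopsis and Appendix A. On the blinded-versus-operating reading, the two surgeons share no item, unit or scale. On either reading, region-level kappa rests on an undefined both-unmarked count.

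Under the assumed counts the resulting range is -0.20 to 0.78. A patient-level version is computable in most outcomes but unstable at 10 per arm: undefined, 0 or -0.11 in the examples above, where raw agreement is 80% or more. The counts are illustrations, not forecasts. The expectation of mostly positive tumours assumes that fluorescence follows the receptor figures cited in section 3.3.

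The consequence is confined to a descriptive secondary endpoint and its hypothesis. The change is worth making because it is cheap, but it is not critical to the trial.

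**What to change.** 1. Reconcile section 8.3.2.3 with the synopsis and Appendix A: state who the raters are and how many.
2. Have every rater in the chosen pair score the same captured photographs on the same added items. These are a yes/no for fluorescence in each of the four photograph sets, by fixed structure (tumour, surrounding kidney and, in Arm 2, the nodal areas or metastases shown), plus the existing five-level brightness item for the tumour. Include an option for a structure not in view, since the tumour is absent from the post-removal set. The free marks can stay as descriptive data.
3. In section 12.8, specify kappa for the yes/no items and weighted kappa for the graded item, with intervals that allow for several photograph sets per patient. Report raw positive and negative agreement alongside, and say what is reported when kappa is undefined.

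If the single blinded surgeon is kept, no extra reader is needed, because the operating surgeon can score the same photographs. That surgeon will have seen the live case, which should be stated when the result is interpreted. If several blinded surgeons are intended, the cost is their reading time. Otherwise the cost is slightly longer forms. Cases already done can be scored from stored images.

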9 TOXICITIES TO BE MONITORED

The safety measures included in this study are standard for studies of investigational drugs. Additional monitoring following administration of study drug is due to screening for a hypersensitivity reaction after administration of OTL38 and for any adverse events that might be related to fluorescent imaging.

Any clinically relevant abnormality (with exception of surgical scars) noted after the start of the study medication that was not present at the screening should be recorded as an adverse event (AE).

On Target, LLC will be notified of any serious adverse events (SAEs) that occur and are felt to be due to the investigational drug by the investigators.

More details about AEs and SAEs can be found in Section 15.

10 STUDY WITHDRAWAL/DISCONTINUATION

Subjects must be discontinued from the study for the following reasons:

- Pregnancy
- Withdrawal of consent

- Investigator deems withdrawal necessary at any time if it is determined that it is not in the subjects best interest to continue or if the subject is found to be noncompliant with study procedures.

If subject discontinues after administration of study drug, he or she will be encouraged to continue on study for safety procedures per protocol. Reason(s) for discontinuing must be clearly documented in the appropriate source documents.

11 DRUG INFORMATION

11.1 Identification and description of test article

OTL38 will be supplied in vials containing 3.0 mL of solution of 2 mg/mL OTL38 for a total of 6 mg of drug per vial.

Study medication should be stored in a freezer at temperature -20°C and with protection from light.

IU Health Investigational Drug Services (IDS) will prepare the IV solutions according to instructions provided by On Target Laboratories at the assigned dose. All solutions should be protected from light.

11.2 Packaging and labeling

The study medication will be packaged in vials and labelled by the Sponsor's clinical supplies designee.

The vial label will include:

Study:

Batch 20802.001Z

OTL38 (6mg in phosphate buffer saline 3ml

Store at -15°C to -25°C

For Clinical Trial Only, Keep out of reach of children

The outer package label will have the following information:

On Target Laboratories, LLC,
[name]
[contact]
Route of administration: injection
Quantity supplied: 6 mg OTL38 per vial
Pharmaceutical dosage form: Phosphate Buffered Saline (pH 7.4)
Storage conditions: keep frozen at temperature -20°C
CAUTION: New Drug – Limited by Federal Law to Investigational Use
Lot number: 20802.001Z
Manufacturing date: 08 October 2013
Retest date: October2015

11.3 Storage and handling of test article

Study medication should be stored in a freezer at -20°C temperature and with protection from light.

11.4 Study drug administration

OTL38 will be prepared following the Dose Preparation for OTL38 Injection Pharmacy Manual (see [Appendix I](#)). OTL38 will be administered intravenously over approximately 60 minutes, less than 2 hours before surgery. If the patient develops any symptoms or signs suggestive of a hypersensitivity reaction, the infusion may be interrupted and then resumed based on the clinical judgement of the investigator on the condition of the patient.

Note that OTL38 should not be mixed with other medicinal products and should not be given simultaneously through the same IV line as another medicine.

11.5 Treatment compliance

All doses of study medication must be prescribed as a written order on each subjects' medical chart in order for IDS to dispense study medication. All doses of study medication are to be administered under the direction of the investigator or physician trained by the investigator.

11.6 Drug accountability

The pharmacist or designee will sign for receipt of study medications upon delivery to IDS. Study medications are to be dispensed only for those subjects formally entered into the study. The actual dosing time of study medication is to be properly documented in the hospital medication administrative record.

At the end of the study, these records will be used to account for all study medication. After drug accountability is reconciled, all unused study medication will be disposed of according to IDS Standard Operating Procedures.

